9.2. Secondary endpoints analyses

The 1st secondary endpoint is defined as attributable mortality at 84 days (12 weeks) follow-up, which will be analyzed in the main analysis population. For this analysis, non-attributable mortality will be considered competing risk for attributable mortality For the analysis of secondary endpoints 2 to 6 see 9.1.

Secondary endpoints 7 and 8 will be analysis using descriptive statistics (6- and 12-week mortality with 95% confidence intervals). If the number of patients in the 2 subgroups described in endpoint 6 and 7 are sufficiently large (\square 25) we will compare the 6 mortality of both groups using the Fisher-Exact test.

Regarding endpoint 9, several studies have studied the impact of galactomannan kinetics on outcome in patients with IA. Studies have shown a reasonable correlation between galactomannan kinetics in the weeks following the initiation of therapy and outcome²¹. However, several questions remain; What is the optimal timing of the follow-up galactomannan measurement? Is the rate of decline more informative than a simpler binary outcome (decline/no decline or decline with 0.5 OD units)? The statistical analysis plan for this endpoint will be written when the study is completed, and the number of galactomannan positive patients and the number of follow-up plasma samples is known.

Secondary endpoints 10 will be analysis using descriptive statistics (6 and 12-week mortality with 95% confidence intervals).

The 11th secondary endpoint is defined as the total duration of the hospital stay. The relation between randomly allocated treatment and this secondary endpoint will be analyzed using a Mann-Whitney U test.

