Another important reason to study upfront combination therapy for patients with IA in the Netherlands and Belgium is the increasing incidence of triazole-resistant A. fumigatus. Indeed, from a global perspective the highest prevalence of triazole resistance has been documented in the Netherlands. It increased from 0% before the year 2000 to 5.3% in 2009, and further increased to 15% in 2017. Unfortunately, more recently triazole resistance was observed in 5% of IA cases in Belgium as well and in 2017 researchers from the Erasme hospital in Brussels even reported a prevalence of 13% (Vermeulen et al., 2015⁵; Montesinos et al., 2017⁶). It has also clearly been demonstrated that the overall mortality becomes very high (50-88%) when patients infected with a triazoleresistant A. fumigatus initially receive inappropriate voriconazole therapy and therapy is only changed at a time when it has become clinically obvious that the IA is progressing (Lestrade et al., 2018⁷, van der Linden et al., 2015⁸; Chong et al., 2015⁹). These important observations recently led to a change in the treatment recommendations of the 2017 Dutch SWAB guideline on fungal infections. In the absence of any evidence from prospective studies on the treatment of IA in regions with a high prevalence of azole resistance, this guideline recommends 2 possible strategies. The first is upfront combination therapy (triazole combined with an echinocandin or liposomal amphotericin B) until resistance can be excluded. The second option, which should only be considered in non-critically ill patients and in centers that are able to perform real-time PCR as well as cultured based resistance testing on BAL samples, is to start with voriconazole monotherapy while waiting for the resistance test (Kullberg et al., 2018¹⁰). Unfortunately, resistance testing will not lead to an interpretable result in approximately 35% of the patients with IA. Indeed, fungal cultures remain negative in the majority of the patients with IA and PCR testing for CYP51 resistance associated mutations is not always successful either. For this subgroup of patients, the SWAB guideline recommends switching from triazole monotherapy to combination therapy as soon as it becomes clear that no resistance result will become available. The latter recommendation has been criticized when it relates to patients that are not very sick and have an infection that is limited to the lungs and that is not widespread. Indeed, some clinicians argue that close monitoring for treatment progression is a valid option as well because the poor outcome of azole resistant IA has not (yet) been convincingly demonstrated for culture negative cases.

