7.1.2. Secondary study endpoints

- 1. Overall aspergillus attributable mortality 12 weeks after the start of antifungal therapy(*).
- 2. Overall survival 12 weeks after the start of antifungal therapy in the MITT population
- 3. Overall survival 6 weeks after the start of therapy in the subgroup of patients in the MITT population with a positive serum galactomannan test at baseline.
- 4. Overall survival 6 weeks after the start of therapy in the subgroup of non-ICU patients who fulfill the EORTC/MSG probable or proven definition (MITT population).
- 5. Overall survival 6 weeks after the start of therapy in the subgroup of non-ICU patients with an underlying haematological disease (MITT population)
- 6. Overall survival 6 weeks after the start of therapy in the subgroup of non-ICU patients without an underlying haematological disease (MITT population)
- 7. Overall survival 6 weeks after the start of therapy in patients that started with triazole monotherapy and in which triazole resistance is detected during follow-up (MITT population)
- 8. Overall survival 6 weeks after the start of therapy in patients that started with triazole-anidulafungin combination therapy and in which triazole resistance is detected during follow-up (MITT population)
- 9. In the subgroup of patients with a positive serum galactomannan; Kinetics of serum galactomannan levels with combination versus monotherapy
- 10. Outcome of patients in which resistance testing was unsuccessful
- 11. Time to hospital discharge (in the MITT subgroup of patients admitted to the hospital at baseline)
- 12. Cost-effectivity of azole-anidulafungin combination therapy
- (*) Aspergillus attributable mortality is defined according to Vidal G et al. (with some modifications) as one of the following²²:

When selecting one of the 4 options below, please consider the immediate cause of death as the disease process, injury, or complication immediately preceding death.

IA is considered the cause of death (=IA attributable mortality)

1. IA was considered the cause of death when the immediate cause of death was due to this infection. Examples are neurological complications of an aspergillus infection

- that disseminated to the brain, lung bleeding or respiratory insufficiency in a patient with pulmonary aspergillosis *or*

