9.5. Sample size calculation

In the pivotal trial on voriconazole and anidulafungin combination therapy the mortality in the voriconazole control group was 28% 6 weeks after the start of therapy. This study only included patients with an underlying haematological disease. Furthermore, in a large pragmatic trial with fewer exclusion criteria and in which a small number of ICU patients will be included as well, we expect a somewhat higher mortality of 35%, We consider a 33% lower overall mortality with combination therapy (=from 35% to 23,33%) compared to monotherapy of clinical importance. This leads to a sample size of 237 evaluable patients per group (=included in the mITT population as defined above) to show superiority of combination therapy compared with monotherapy with an alfa of 0.05 and a power of 80%. Follow-up for the primary endpoint is 6 weeks after the start of antifungal therapy.

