10. COST-EFFECTIVENESS ANALYSIS

The cost-effectivity of combination therapy compared with triazole monotherapy will be analyzed only if a statistical difference (p0.05 or lower) is observed for the primary endpoint or for secondary endpoint 2. The full statistical analysis plan for endpoint 12 is therefore not yet complete but will be developed after the analysis of these endpoints has been completed and in collaboration with prof. dr. [name] of the institute of Medical Technology Assessment in Rotterdam (iMTA). The analysis will estimate if combination therapy is cost saving and if this is not the case the cost per quality adjusted life year of combination therapy compared to monotherapy will be calculated. For this, not only quality of life data, the (time to) death but also detailed data on each of the following clinical parameters that are associated with substantial increase in costs will be collected; Duration of hospital stay and number of days admitted to the intensive care unit, blood products and antifungal drugs administered as well as enteral or parenteral nutrition given between baseline and week 12 of follow-up. For the quality of life data collection, the EuroQOL EQ5D-5L questionnaire will be used (including the proxy or telephone version if needed, appendix 5). Because the majority of the patients with IA in our study will consist of patients treated for AML with intensive chemotherapy and of patients that received an allogeneic stem cell transplantation, previously published utility scores from these patient populations will be used to calculate the cost per quality adjusted life years gained (QALY) with combination therapy compared with monotherapy. 19 Apart from quality of life data, we will collect data on loss of income up to 24 weeks after inclusion to allow for an analysis of cost-effectivity from the society perspective. For this purpose, a set of dedicated questionnaires will be used (appendix 5).

The study population will consist of 3 major study populations: Patients receiving chemotherapy for AML, patients with graft-versus-host-disease and other patients. If a significant treatment effect of the intervention is observed in one of these subgroups, an exploratory cost-effectiveness analysis will be done for this subgroup.

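### Fisher's exact test for the resistant-infection comparison runs at about 3% or less instead of 5% when groups number 25 to 35; Boschloo's exact test on the same day-42 outcome recovers some power at no cost

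*Protocol*

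**What the plan says.** Secondary objective 2 asks how patients with a triazole-resistant *A. fumigatus* fare by initial therapy, and it maps to secondary endpoints 7 and 8. Section 7.1.2 defines these at a fixed time point; endpoint 7 begins "Overall survival 6 weeks after the start of therapy in patients that started with triazole monotherapy", and endpoint 8 is its counterpart for combination therapy.

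Section 9.2 sets the analysis in two steps. The main one is descriptive: "Secondary endpoints 7 and 8 will be analysis using descriptive statistics (6- and 12-week mortality with 95% confidence intervals". The second is conditional: "If the number of patients in the 2 subgroups described in endpoint 6 and 7 are sufficiently large" (the comparison sign before 25 did not survive text extraction; I read it as at least 25 in each group), then "we will compare the 6 mortality of both groups using the Fisher-Exact test". The missing unit is plainly weeks. The numbering is off by one, since endpoints 7 and 8 are meant.

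No power, effect size or expected group size is given for this comparison.

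**The concern.** Resistance is one of the protocol's stated reasons for the trial, and this is the only between-group test for it. The number of resistant patients is set by prevalence and cannot be raised by design, so the choice of test is one of the few things the sponsor can improve.

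Fisher's test conditions on the total number of deaths. In small groups only a few tables are then possible, and the attained error rate falls well below the nominal one. The test gives up power without being any more valid than an exact test that comes closer to 5%. A real difference is therefore somewhat more likely to be reported as non-significant than it needs to be.

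**Working it through.** **The plan's own figure.** The only sample size in the protocol is for the primary endpoint (9.5): 35% v 23.33%, two-sided 5%, 80% power. With pooled variance and mean rate 0.29165:

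n = [1.96 √(2 × 0.29165 × 0.70835) + 0.8416 √(0.35 × 0.65 + 0.2333 × 0.7667)]² / 0.1167² = 236.9, so 237 per group. It reproduces.

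**Inputs for the resistant comparison.**
- Group size: 25 is the floor for running the test. Taking 5% (Belgium) to 15% (Netherlands) resistance from section 1 and applying it to 474 patients gives 474 × 0.05 / 2 = 12 to 474 × 0.15 / 2 = 36 per arm. This is rough, because resistant patients come on top of the MITT. If the test runs at all, about 25 to 36 per group is plausible. I used equal groups of 25, 30 and 35.
- Monotherapy mortality: assumed. I spanned 50% to 88% because it is the only range the protocol prints for resistant disease, and added 35% and 40% as lower values.
- Effect: assumed. I used the trial's own relative reduction ("We consider a 33% lower overall mortality with combination therapy (=from 35% to 23,33%) compared to monotherapy of clinical importance"), with 50% as a sensitivity.
- Two-sided 5%, as 9.3 states for the primary endpoint.

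**Method.** For deaths a and b in two groups of n, let p_F(a,b) be Fisher's two-sided p-value.
- Size at a common death rate π: Σ Bin(a; n, π) Bin(b; n, π) over all tables with p_F ≤ 0.05.
- Power: the same sum with π₁ and π₂.
- Boschloo: p_B = the maximum over π of the probability, under equal rates, of a table with p_F no larger than the one observed. Since p_B ≤ p_F always, every table that Fisher rejects is also rejected by Boschloo.

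**True size, maximum over π.**

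| n per group | Fisher | Boschloo |
|---|---|---|
| 25 | 0.033 | 0.046 |
| 30 | 0.027 | 0.047 |
| 35 | 0.029 | 0.048 |

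At n = 25 Fisher's size is 0.033 at a 50% death rate, 0.022 at 75% and 0.013 at 88%.

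**Power, Fisher to Boschloo, 33% relative reduction.**

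| Mortality | n = 25 | n = 30 | n = 35 |
|---|---|---|---|
| 50 v 33% | 0.17 to 0.20 | 0.18 to 0.25 | 0.21 to 0.27 |
| 60 v 40% | 0.24 to 0.25 | 0.26 to 0.33 | 0.28 to 0.36 |
| 69 v 46% | 0.31 to 0.35 | 0.34 to 0.43 | 0.40 to 0.47 |
| 75 v 50% | 0.36 to 0.44 | 0.41 to 0.50 | 0.50 to 0.57 |
| 88 v 59% | 0.54 to 0.65 | 0.66 to 0.70 | 0.74 to 0.81 |

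With a 50% reduction the gain is 1 to 9 points. From 35% or 40% mortality with a 33% reduction it is 3 to 6 points, and power stays at or below about 0.21. Overall the gain at 25 to 35 per group is about 1 to 11 points.

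**One table.** With 19 of 25 v 12 of 25 deaths (76% v 48%), Fisher gives p = 0.079 and Boschloo p = 0.046.

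**Log-rank as a comparison.** At n = 25, with simulated survival censored at day 42 and the same monotherapy rates, the gain over Fisher is 6 to 21 points under proportional hazards and about 0 to 6 if the effect appears only after day 14. At n = 50 with a late effect it ranges from +3 to −3 points.

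**The case against.** Fisher's test is a standard, valid choice for a small 2×2 table. The comparison is conditional and secondary, carries no power claim, and sits behind a descriptive analysis whose confidence intervals do most to answer the objective. Even with a better test, power is mostly below 60% for a one-third reduction. All of this stands and limits the weight of the point. It does not remove it, because the replacement answers the same question on the same data with the same error guarantee and is never less powerful.

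A reader might go further and infer that the dead/alive cut is the fault, that a log-rank test should replace Fisher, and that the plan forfeits 8 or more points of power. The documents do not support this.
- Section 1 says "the overall mortality becomes very high (50-88%) when patients infected with a triazoleresistant A. fumigatus initially receive inappropriate voriconazole therapy", but ties that range to therapy changed only once progression is clinically obvious. This trial offers resistance testing so that therapy can be redirected earlier. The protocol states no expected mortality for resistant patients managed that way.
- Eight points is not a floor. The log-rank gain is about 5 to 7 points at lower mortality and can vanish with a late effect. Proportional hazards is doubtful when therapy is redirected during follow-up.
- Much of the loss is Fisher's conservatism, not the binary cut. At 69% v 46% and n = 25, power is 0.31 with Fisher, 0.42 with a plain chi-square on the same binary outcome and 0.40 with log-rank.
- Endpoints 7 and 8 are defined as survival at 6 weeks. A log-rank test addresses a different quantity.
- Twenty-five is the minimum for running the test, not the planned size.

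**Conclusion.** The point holds as a small efficiency defect. At 25 to 35 per group the test named in 9.2 has a true two-sided size of at most about 3%. Boschloo's test on the same outcome stays at or below 5% and gains about 1 to 11 points of power.

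The size results need only equal groups and a nominal two-sided 5%. The power gains also rest on assumed mortality rates and effects, and they shrink in larger groups (about 0 to 6 points at 50 per group). Nothing here makes the planned test invalid or touches the primary analysis. A non-significant result remains likely in many scenarios after the change.

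**What to change.** In 9.2, for the comparison of endpoints 7 and 8:
- Replace Fisher's exact test with Boschloo's unconditional exact test, two-sided at 5%, on death by day 42 and grouped by initial randomised therapy.
- Keep the 6- and 12-week mortality with 95% confidence intervals as the main summary.
- Correct the cross-reference from endpoints 6 and 7 to 7 and 8, and write 6-week mortality. While there, reconcile the MITT label on endpoints 7 and 8 in 7.1.2 with 7.1.4, which removes documented voriconazole resistance from the MITT.
- Optionally, add a log-rank test of time to death to day 42 as a supportive analysis. Section 10 already lists time to death among the data collected. Its extra gain depends on mortality level and hazard shape, so it should not replace the day-42 comparison.

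The cost is one or two sentences before the data are analysed. No new data or patients are needed, and Boschloo's test is available in standard software.

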2. OBJECTIVES

Primary objective

1. Evaluate if the survival in patients with a triazole susceptible IA can be improved when the initial therapy consists of triazole and echinocandin combination therapy instead of triazole monotherapy. This objective is captured in the primary endpoint as well as secondary endpoints 1 to 6)

Secondary objectives

- 1. Evaluate if a triazole/echinocandin combination therapy improves the overall quality of life and if it is a cost-effective intervention (these objectives are captured in secondary endpoint 11 and 12)
- 2. Evaluate the outcome of patients in which a triazole-resistant A. fumigatus is detected in relation to the initial antifungal therapy they had received (i.e. triazole monotherapy or combination therapy). This objective translates into secondary endpoint 7 an 8.
- 3. Evaluate the outcome of patients in which resistance testing is unsuccessful in function of the antifungal therapy they received. This translates into secondary endpoint
- 4. Evaluate if the baseline serum galactomannan value and the serum galactomannan kinetics are predictive of overall 6-week survival. This translates into secondary endpoint 3 and 9.

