3. STUDY DESIGN

A non-blinded phase 3 multicenter randomized pragmatic clinical trial.

Intervention: Add anidulafungin IV to the standard of care therapy that consists of a triazole (voriconazole or isavuconazole or posaconazole).

In both the intervention and control group, the triazole will be given for at least 6 weeks. In the intervention group the echinocandin will be discontinued after 28 days but when a treatment response is observed and the patients can be discharged from the hospital, the echinocandin can be discontinued from day 7 onwards according to the choice of the treating physician. Figure 1 illustrates the study design and the patient flow in the study. The youtube presentation https://www.youtube.com/watch?v=Knq58Zar4hY also clearly explains this flowdiagram.

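### The galactomannan kinetics plan (endpoint 9) is to be written after study completion, with measure and time point open and nothing requiring it to be fixed before outcomes are seen

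*Protocol*

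**What the plan says.** Protocol Section 7.1.2 defines endpoint 9, in patients with a positive serum galactomannan, as "Kinetics of serum galactomannan levels with combination versus monotherapy". It is a comparison of the randomised arms. Section 2 also assigns endpoint 9, with endpoint 3, to secondary objective 4. That objective asks whether the baseline value and "the serum galactomannan kinetics are predictive of overall 6-week survival".

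Section 9.2 then raises two questions as unresolved. The first is "What is the optimal timing of the follow-up galactomannan measurement". The second is "Is the rate of decline more informative than a simpler binary outcome (decline/no decline or decline with 0.5 OD units". On when they will be settled it says "The statistical analysis plan for this endpoint will be written when the study is completed", and adds as a condition that "the number of galactomannan positive patients and the number of follow-up plasma samples is known".

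Section 3 describes the design as "A non-blinded phase 3 multicenter randomized pragmatic clinical trial". Section 9.6 makes the coordinating investigator responsible for the data analysis. For cost-effectiveness (endpoint 12), Section 10 says that the full plan "will be developed after the analysis of these endpoints has been completed", meaning the primary endpoint and secondary endpoint 2.

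**The concern.** This is not a detail left to a statistical analysis plan that is not shown. The Protocol itself sets when the plan for this endpoint is written, and sets it late. A separate plan that followed this text would leave endpoint 9 open too.

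The two open choices, which day and which measure of decline, largely determine what an analysis of kinetics will show. If they are made by people who can see allocation and deaths, a between-arm difference may appear because the day or cut-off that showed it was the one chosen. In the prognostic analysis, picking the day and cut-off that best separate survivors from non-survivors makes prediction look better than it is. At stake is how far either result of endpoint 9 can be believed.

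**Working it through.** **1. What will be known when the plan is written.**

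- Allocation: known throughout, because the trial is non-blinded (Sections 3 and 7.2).
- Survival: Appendix 2 records survival status to D168, and Section 12.5 defines the end of the study as the last patient's last visit. The 6-week and 12-week survival data will therefore have been collected by study completion.
- Galactomannan values: not determinable. Appendix 2 refers to storage of serum under an appendix that is not shown, so the assays may come later.
- Safeguard: no section requires the endpoint 9 plan to be fixed before database lock, before survival by arm is seen, or by someone unaware of allocation and outcome.

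**2. Whether the stated reason needs the delay.** The condition is the number of galactomannan-positive patients and of follow-up samples. Both are pooled counts. They can be tabulated without arm or outcome, before the database is locked.

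**3. Illustrative size.** The Protocol gives no figure for endpoint 9, so there is none to reproduce. Its one design calculation is for the primary endpoint in Section 9.5 (35% versus 23.33%, two-sided 0.05, power 80%). That reproduces at 237 per group with the pooled-variance formula and is not touched by this point.

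Inputs for the illustration:

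- Follow-up serum days after baseline: D3, D5, D7, D14, D28, so 5 (Appendix 2).
- Measures named in Section 9.2: rate of decline, any decline, decline by 0.5 OD, so 3.
- Assumed, not in the Protocol: every measure is tested between arms on every day at two-sided 0.05, giving 3 × 5 = 15 tests, with a common correlation ρ between the test statistics.

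Under independence the chance of at least one p<0.05 with no effect is 1 − 0.95^k:

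- k = 3 (three measures, one day): 1 − 0.95³ = 14.3%
- k = 5 (one measure, five days): 1 − 0.95⁵ = 22.6%
- k = 15: 1 − 0.95¹⁵ = 53.7%

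With common correlation ρ and c = 1.96, the chance is 1 − ∫ φ(u) [Φ((c − √ρ·u)/√(1−ρ)) − Φ((−c − √ρ·u)/√(1−ρ))]^15 du. Numerical integration gives:

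| Assumed ρ | Chance of at least one p<0.05 in 15 tests |
|---|---|
| 0.9 | 14.4% |
| 0.7 | 25.6% |
| 0.5 | 36.1% |
| 0 | 53.7% |

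As a second check, repeated optical-density values were simulated with no treatment effect. The assumptions were 50 or 100 positive patients per arm, log-normal values, within-patient correlation 0.3 to 0.9 and no missing samples. At least one of the 15 tests reached p<0.05 in 37% to 40% of runs. With the rate measure alone over five days it was 18% to 20%. With one measure and one day fixed in advance, the chance is the nominal 5%.

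**The case against.** **No confirmatory claim is at risk.** Section 9.3 gives a significance level only to the primary endpoint. Endpoint 9 is one of twelve secondary endpoints, and no test, alpha or interval is promised for it. A reader might infer that stated p-values are invalidated; the Protocol states none here. This stands and limits the severity. It does not remove the point, because Section 7.1.2 still lists endpoint 9 as an arm comparison, and the exploratory label in Section 9.1 is written for endpoints 2 to 6.

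**The plan is not said to be written in view of the outcomes.** The stated condition is sample counts, and a completed study is not yet an analysed one. A reader might infer an intention to choose after seeing results; the text does not support that. What stands is the opportunity: survival and allocation will be on file, and nothing bars their use.

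**The open questions are research questions.** Section 9.2 raises them from the literature on kinetics and outcome, and the best timing can be found only by comparing days against survival. Fixing a single day for everything would drop a question the Protocol means to ask. This stands, so the two aims need separate treatment.

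**The grid of 15 is an assumption.** A rate of decline could be one slope per patient over all samples, a 0.5 OD decline is a subset of any decline, and all measures share the same values. Serum is also taken only from patients in hospital or attending clinic, so the days will not be equally usable. This stands: 54% is not realistic, and the other figures are illustrations.

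**Cost-effectiveness is largely specified.** A reader might infer that its plan is wholly deferred. Section 10 already fixes the outcome (cost saving, otherwise cost per QALY), the EQ-5D-5L, the resource items and the condition for running the analysis. Only the remaining methods are postponed.

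**Conclusion.** The point holds as a weakness in the timing rule of Section 9.2. The endpoint 9 plan is deferred to study completion with day and measure open, in a non-blinded trial, and no safeguard keeps the choice independent of survival and allocation. Both the arm comparison and the prognostic analysis for objective 4 could be data-driven.

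The size depends on choices the Protocol does not make. On the assumed grid, the nominal 5% becomes roughly 14% to 36% for correlations from 0.9 down to 0.5. Fewer candidate analyses would give less.

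The primary endpoint, its sample size and its test are unaffected. The change is worth making because it is cheap and cannot be made once results have been seen. The Section 10 deferral is a minor companion point, and the figures above say nothing about it.

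**What to change.** Replace the deferral sentence in Section 9.2 with a rule that the endpoint 9 plan is finalised and dated before database lock, and before any survival or galactomannan result by arm is reviewed. It should use only pooled, arm-blind counts of galactomannan-positive patients and samples. The plan should:

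- name one main measure and one time point, of the sponsor's choosing, for the between-arm comparison;
- treat the search for the best timing or measure against survival as a separate analysis, labelled exploratory;
- say how deaths before the sampling day are handled, for example by a landmark at that day for the survival question, and how missing samples are handled.

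The futility review in Section 7.7 may show the study team mortality by arm at half the sample. If the plan is not final by then, someone without access to that review should write it.

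As a minor addition, complete the remaining Section 10 methods before survival results by arm are known, and keep the existing condition for running that analysis.

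The cost is writing the same document earlier, plus a protocol amendment. No extra patients, visits or samples are needed.

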9.4. Missing data

Patients that are lost to follow-up after the start of study drugs will be considered treatment failures in the mITT analysis.

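### Endpoint 11 has two definitions, and its Mann-Whitney comparison of length of stay has no rule for in-hospital death, so the result depends on when patients die

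*Protocol*

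**What the plan says.** Section 7.1.2 of the protocol lists endpoint 11 as "Time to hospital discharge (in the MITT subgroup of patients admitted to the hospital at baseline". Section 9.2 gives a different variable, "The 11th secondary endpoint is defined as the total duration of the hospital stay", and fixes the method: "The relation between randomly allocated treatment and this secondary endpoint will be analyzed using a Mann-Whitney U test".

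Neither section assigns a value to a patient who dies before discharge. The missing-data rule in section 9.4 covers loss to follow-up only: "Patients that are lost to follow-up after the start of study drugs will be considered treatment failures in the mITT analysis". It does not mention death and gives no length-of-stay value.

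For endpoint 1, section 9.2 does deal with a competing event: "non-attributable mortality will be considered competing risk for attributable mortality". Section 9.5 plans a fall in 6-week mortality "from 35% to 23,33" per cent, with 237 evaluable patients per group. Section 2 assigns endpoints 11 and 12 to the objective on quality of life and cost-effectiveness.

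**The concern.** The two definitions are different variables. Time to discharge ends when the patient leaves hospital. Total length of stay can also end in death. It might also include days before randomisation or readmissions, since Appendix 2 registers hospital days up to week 24.

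Under the section 9.2 definition, a patient who dies on day 8 has an 8-day stay and receives the same rank as one who goes home well on day 8. The plan expects roughly a quarter to a third of patients to die by week 6, and unequally between arms. The comparison therefore mixes speed of recovery with timing of death. If deaths tend to precede discharges, an arm that saves lives has fewer short stays and appears to do worse on endpoint 11. Under section 10, endpoint 12 is analysed only if mortality differs at week 6 or week 12. Endpoint 11 is thus most open to distortion when it would be read beside a survival benefit.

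**Working it through.** **Planning figure.** The inputs are 35% and 23.33% mortality, two-sided alpha 0.05 and 80% power (sections 9.3 and 9.5). The mean proportion is 0.29165, and with pooled variance:

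n = [1.960 × √(2 × 0.29165 × 0.70835) + 0.8416 × √(0.35 × 0.65 + 0.2333 × 0.7667)]² / 0.1167² = (1.260 + 0.537)² / 0.01362 ≈ 237 per group.

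This reproduces the protocol's figure, so the mortality inputs can be carried forward.

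**Model for endpoint 11.** The protocol gives no distribution of stay or time of death, so the following are assumptions:
- survivors' stay is lognormal, median 25 days, log-SD 0.6, identical in both arms;
- death times are lognormal with the same log-SD, and the median is varied;
- all 237 per arm are inpatients and all deaths occur in hospital.

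Let q be the probability that a random survivor's stay exceeds a random death time:

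q = Φ( ln(25 / median death day) / (0.6 × √2) ).

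The two arms differ only in their proportion of deaths. The Mann-Whitney quantity θ, the probability that a stay on combination exceeds one on monotherapy, is therefore

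θ = 0.5 + (0.35 − 0.2333) × (q − 0.5).

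Its null standard error is √[(2 × 237 + 1) / (12 × 237²)] = 0.02655. The chance of a significant result for monotherapy (shorter stays) is about Φ((θ − 0.5)/0.02655 − 1.96).

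For a median death day of 12: ln(25/12) = 0.734; q = Φ(0.734/0.8485) = 0.806; θ = 0.5 + 0.1167 × 0.306 = 0.536; Φ(1.35 − 1.96) ≈ 27%.

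| Median death day (assumed) | q | θ | Significant for monotherapy, formula | Same, simulated |
|---|---|---|---|---|
| 7 | 0.933 | 0.551 | 48% | 48% |
| 12 | 0.806 | 0.536 | 27% | 28% |
| 15 | 0.726 | 0.526 | 17% | 17% |
| 20 | 0.604 | 0.512 | 7% | 8% |
| 25 | 0.500 | 0.500 | 2.5% | 2.8% |
| 30 | 0.415 | 0.490 | 1.0% | 1.1% |

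The nominal rate in this direction is 2.5%. At day 30 the lean is the other way: Φ(0.37 − 1.96) ≈ 5.6% of trials significantly favour combination.

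**Second model.** Here death interrupts a stay at a constant hazard matched to 35% and 23.33% by day 42, and time to discharge is identical in both arms. Log-SD is 0.7 and not all deaths fall in hospital. With median time to discharge of 14, 21 or 28 days (assumed), simulation gives 10%, 18% and 29% of trials significantly favouring monotherapy, and 0.4% or fewer favouring combination.

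**Reversal.** In the first type of model with log-SD 0.7, a median stay of 14 days and median death day of 21 to 28, about 10% to 20% of simulated trials significantly favour combination although survivors' stays are identical.

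**The case against.** **Direction.** A reader might infer that the better-surviving arm must look worse. The documents do not support this, because they give no distribution of stay or time of death. The direction holds when deaths tend to come earlier than discharges. It disappears when the two coincide and reverses when deaths come later. This objection stands, and the conclusion is conditional for that reason.

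**Size.** The figures are an upper bound. Section 7.1.2 restricts the endpoint to patients in hospital at baseline, and Appendix 2 expects some outpatients. With 180 inpatients per arm (assumed) and median death day 12, the 28% becomes about 22%. With the earlier randomised trial's mortality quoted in section 6.2 (27.8% versus 19.5%), the rates are about 16%, 10% and 6% for death days 12, 15 and 20. This also stands.

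**Estimand.** Bed-days used, including by patients who die, are a proper quantity for resource use, and section 10 collects them for that purpose. That justifies keeping them for endpoint 12. It does not justify using them as a test of time to discharge.

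**Deferral to an SAP.** A separate plan might add a scoring rule for deaths. However, section 9.2 already fixes the variable and the test. Where the protocol postpones analysis detail, for endpoints 9 and 12, it says so.

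**Ranking deaths worst.** A reader might infer that keeping the rank test and scoring deaths as the worst outcome would give a clean test of length of stay. It would not. With identical survivor stays, that version favours combination in about 60% of simulated trials, on mortality alone. With equal mortality and survivors leaving 10% earlier, it detects the difference in about 15% of trials, against 22% for the planned test.

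**Conclusion.** The point holds in conditional form. Sections 7.1.2 and 9.2 define endpoint 11 differently. The fixed analysis has no rule for in-hospital death, although section 9.2 recognises a competing event for endpoint 1. Under the planned mortality and no difference in survivors' stays, about 8% to 28% of trials would significantly favour monotherapy for an assumed median death day of 20 down to 12 and median survivor stay of 25 days. That is an upper bound on the inpatient and in-hospital-death assumptions, and later deaths remove or reverse the bias. Whichever way it leans, the result would partly reflect when patients die rather than how quickly they recover.

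This should be corrected, but it is not critical. Endpoint 11 is one of twelve secondary endpoints and is not confirmatory. The primary analysis and the sample size are unaffected, and mortality is reported in its own right.

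**What to change.** Use one definition in sections 7.1.2 and 9.2: time from randomisation to discharge alive, in MITT patients in hospital at baseline. Treat in-hospital death as a competing event, show cumulative incidence of discharge alive by arm, and compare with Gray's test or a Fine-Gray model. Report it beside mortality. Keep raw hospital days, deaths included, as a resource-use input for endpoint 12.

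The downside is small: discharge alive partly reflects mortality, so the text should say that it is not an effect on survivors' length of stay.

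The cost is mainly wording, best settled before outcome data are seen. Appendix 2 already schedules hospital days and survival status. The sponsor should confirm that the eCRF holds the date of first discharge and whether a death occurred before it.
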